4.7 Inclusion Criteria

- male and female subjects aged between 18 and 70 years;
- subjects with lateral palpatory pain that has appeared for at least 1 month;
- subjects with pain symptoms of the hip assessed according to the Numerical rating scale (NRS) ≥ a 5;
- subjects who are able to cooperate with the assessments in the investigation plan;
- Subjects able to understand and sign informed consent.
- (NB. Subjects with bilateral hip pain symptoms will be included for the more symptomatic side and treated monolaterally).

4.8 Exclusion Critera

- subjects suffering from true coxalgia (with positive FADDIR)
- subjects suffering from ESHS (external snapping hip syndrome);
- subjects who have already undergone hip replacement surgery as a candidate for treatment;
- subjects with radiological and clinical evidence of detachment of the tendons of the lesser and/or middle gluteus with an indication for surgical repair;
- subjects with evidence of radiographically documented tendon calcifications;
- subjects with a degree of coxarthrosis of the hip that is a candidate for treatment according to the Tonnis>1 classification
- subjects who have taken fluoroquinolones within 30 days prior to enrolment
- subjects who have undergone treatment with hyaluronic acid or corticosteroids in the hip candidate for infiltrative treatment within 4 weeks prior to enrolment
- subjects with local or systemic infections of the candidate hip, osteomyelitis or sepsis;
- subjects undergoing chronic treatment with corticosteroids or immunosuppressants;
- subjects who are drug addicts, alcoholics, suffer from psychiatric disorders or have clinical conditions that may compromise the correct interpretation of PROMs or follow-up;
- subjects with coagulopathies, platelet aggregation disorders or those on oral anticoagulants or antiplatelet agents that cannot be discontinued during the study period
- pregnant and lactating subjects (female subjects of childbearing age must be tested for pregnancy prior to enrolment)
- subjects with an allergy to porcine collagen.

MEDANTRO" CLINICAL INVESTIGATION PLAN Version 2.5 of 08 January 2021 MDG2020711

4.9 Coding of the subjects

At the time of enrolment, each subject shall be assigned a complex alphanumeric identification code consisting of the progressive enrolment number followed by an alphanumeric code generated by GUNA S.p.a. through *Random Sequence Generator* (www.random.org).

The complex code complies with the current Privacy Law on the coding of subjects participating in clinical trials.

4.10 Procedures

4.10.1 Evaluation Time

T0 baseline: Enrolment and start of infiltrative treatment

Week T1: Second infiltrative treatment T2 weeks: Third infiltrative treatment

T6 weeks/FU Follow-up visit
T10 weeks/FU Control visit
T24 weeks/FU Follow-up visit

4.10.2 Visit Paln

TO BASAL: Enrolment

In the course of daily clinical activity, investigators participating in the Clinical Ivestigation Plan will select subjects with GTPS. The Principal Investigator will be responsible for the correct clinical diagnosis, also making use of the instrumental examinations provided for in the Investigation Plan. Subjects meeting the inclusion and exclusion criteria will thus be identified. After having thoroughly explained the aims, purposes and procedures foreseen by the Investigation Plan, the subject will be proposed to participate in the Investigation itself. Finally, the selected subject will be asked to read the information form and to date and sign the Informed Consent and Consent to the Processing of Personal Data form.

Female subjects will have to provide evidence of a negative pregnancy test in order to be enrolled.

We will then proceed with the objective examination and the collection of the information required by the electronic Data Collection Form appropriately prepared.

This will be followed by:

- pain assessment using the NRS scale;
- assessment of pain using the Modified Harris Hip Score (mHHS) scale;
- clinical assessment of pain on palpation of the trochanter using the NRS scale;
- clinical assessment of stenia in abduction of the lower limb with the dynamometer;
- clinical assessment of phlogistic-degenerative signs by MRI of the peritrochanteric region;

The first infiltration will then be performed by means of ultrasound.

Previous or ongoing pharmacological treatments of any kind will be documented.

In order to monitor the consumption of analgesic (celecoxib 200mg / paracetamol 1000 mg) used during the investigation in the event of the onset of pain, a clinical diary will be given to the subject in which to indicate the day and the dose of drug used.

The enrolled subject will be assigned an identification code of a complex type formed by the progressive enrolment number followed by an alphanumeric code generated by GUNA S.p.a. through *Random Sequence Generator* (www.random.org.)

TO BASAL: Enrolment

In the course of daily clinical activity, investigators participating in the Survey will select subjects with GTPS. The Principal Investigator will be responsible for the correct clinical diagnosis, also making use of the instrumental examinations provided for in the Investigation Plan. Subjects meeting the inclusion and exclusion criteria will thus be identified. After having fully explained the aims, purposes and procedures foreseen by the Investigation Plan, the subject will be proposed to participate in the Investigation itself. Finally, the selected subject will be asked to read the information form and to date and sign the Informed Consent and Consent to the Processing of Personal Data form.

Female subjects will have to provide evidence of a negative pregnancy test in order to be enrolled.

We will then proceed with the objective examination and the collection of the information required by the electronic Data Collection Form appropriately prepared.

This will be followed by:

- pain assessment using the NRS scale;
- assessment of the Modified Harris Hip Score (mHHS) scale;
- clinical assessment of pain on palpation of the trochanter according to the NRS scale;
- clinical assessment of stenia in abduction of the lower limb with the dynamometer;
- clinical assessment of phlogistic-degenerative signs by MRI of the peritrochanteric region;

The first infiltration will then be performed by means of ultrasound.

Previous or ongoing pharmacological treatments of any kind will be documented.

In order to monitor the consumption of analgesic (celecoxib 200mg / paracetamol 1000 mg) used during the investigation in the event of the onset of pain, a clinical diary will be given to the subject in which to indicate the day and the dose of drug used.

The enrolled subject will be assigned an identification code of a complex type formed by the progressive enrolment number followed by an alphanumeric code generated by GUNA S.p.a. through Random Sequence Generator (www.random.org.)

T1 week:

At 7 days from day 0, the second infiltration will be performed, the use of celecoxib or paracetamol will be assessed through clinical diary analysis and any Adverse Events occurring after the first administration will be evaluated.

T2 weeks:

At 14 days from day 0, the third infiltration will be performed, celecoxib or paracetamol utilisation will be assessed through clinical diary analysis and any Adverse Events occurring since the last administration will be evaluated.

T6 weeks/FU:

At 6 weeks from day 0, the endpoints in the Investigation Plan will be assessed.

Including:

- pain assessment using the NRS scale;
- assessment of the mHHS scale;
- clinical assessment of pain on palpation of the trochanter using the NRS scale;
- clinical assessment of stenia in abduction of the lower limb with the dynamometer;
- assessment of analgesic drug consumption when pain occurs
- through clinical diary;
- evaluation of any Adverse Events.

T10 weeks/FU:

At weeks 10 from day i.e. weeks 8 after the end of the treatment, the assessment of the end points in the Clinical Investigation Plan will be carried out again.

Including:

- pain assessment using the NRS scale;
- assessment of the mHHS scale;
- clinical assessment of pain on palpation of the trochanter using the NRS scale;
- clinical assessment of stenia in abduction of the lower limb with the dynamometer;
- assessment of analgesic drug consumption when pain occurs
- through clinical diary;
- evaluation of any Adverse Events.

T24 weeks/FU:

At 24 weeks from day 0 at the end of the Clinical Investigation, all the endpoints of the Investigation Plan will be assessed.

Including:

- pain assessment using the NRS scale
- assessment of the mHHS scale;
- clinical assessment of pain on palpation of the trochanter using the NRS scale;
- clinical assessment of stenia in abduction of the lower limb with the dynamometer;

- clinical evaluation and recording by MRI of signs of the inflammatory and degenerative state of the peritrochanteric region of the hip affected by GTPS.
- evaluation of analgesic drug consumption when pain occurs
- through clinical diary;
- evaluation of any Adverse Events.

Diagnosis, evaluation of inflammatory and degenerative signs on MRI examination of the hip affected by GTPS and evaluation of pain on palpation of the trochanter will be carried out by [name]. The NRS and mHHS rating scales will be administered to the subject by a Co-Investigator. The evaluation of the lower limb abduction stenia will be carried out by a Co-Investigator, by means of a dynamometer, with which three measurements will be taken (with a recovery of 1 minute between each measurement) from which the average will be derived for a more accurate evaluation. The recording of the data in the clinical diary concerning the intake of celecoxib or paracetamol will be performed by the Co-Investigator.

The occurrence of Adverse Events will be assessed at each visit. All Adverse Events (AEs), Serious Adverse Events (SAEs) and Suspected Serious and Unexpected Adverse Reactions (SUSARs) occurring between the date of signing the Informed Consent and the end of the Clinical Investigation will be recorded and reported.

All data collected will have to be entered by the Principal Investigator or a Co-Investigator identified by the Principal Investigator into the Electronic Data Collection Sheet provided by Guna S.p.a.

In particular, it is planned to obtain a data collection that is schematically described in the following table (Tab. 1), in which the entries to be made at each visit are shown:

PROCEDURE	VISIT	VISIT	VISIT	VISIT	VISIT	VISIT
SPERIMENTALI						
	Т 0	T 1	T 2	T 6/FU	T10/FU	T24/FU
		WEEKS	WEEKS	WEEKS	WEEKS	WEEKS
	enrolment	Visit	Visit	Control visit	Control visit	End of Clinical
	1°	2°	3°			Investigation
	infiltration	infiltration	infiltation			
Clinical diagnosis of	X					
GTPS						
Evaluation of Selection	X					
Criteria						
Signature of informed	X					
consent						
Signature of consent to	X					
personal data						

processing						
Collection of socio-	X					
demographic data						
Medical history	X					
collection						
NRS Evaluation	X			X	X	X
Assessment of pain on	X			X	X	X
palpation according to						
NRS						
mHHS assessment	X			X	X	X
Assessment of stenia in	X			X	X	X
abduction						
Evaluation of phlogistic	X					X
and degenerative signs						
on MRI						
Infiltrative Treatment	X	X	X			
Evaluation of clinical	X	X	X	X	X	X
diary						
Adverse Event	X	X	X	X	X	X
Evaluation (AE/SAE)						

Tab.1 Data collection during the Clinical Investigation Plan

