4.12 Study group

• Group (Collagen Medical Device):

Experimental group will be treated with 2 ml volume ultrasound-guided infiltrations of:

• MD-Tissue (GUNA, Milan-Italy)

Composition per 2 ml: collagen 100 micrograms

Excipients: Ascorbic acid, Magnesium gluconate, Pyridoxine hydrochloride, Riboflavin, Thiamine hydrochloride, NaCl, Water for injection.

Subjects will be treated with 1 ultrasound-guided infiltration per week for 3 consecutive weeks.

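### The first scheduled adverse-event check after the day of the third infiltration comes 28 days later, against 7 days for the first two, so brief reactions to it may be under-recorded

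*Combined protocol and SAP*

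**What the plan says.** Section 4.12 sets the treatment course: "Subjects will be treated with 1 ultrasound-guided infiltration per week for 3 consecutive weeks". Section 4.10.2 places the infiltrations at T0, T1 and T2 and describes what is asked about adverse events at the later visits:

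- **T1.** "At 7 days from day 0, the second infiltration will be performed", and "any Adverse Events occurring after the first administration will be evaluated".
- **T2.** "At 14 days from day 0, the third infiltration will be performed", and "any Adverse Events occurring since the last administration will be evaluated".
- **T6.** "At 6 weeks from day 0, the endpoints in the Investigation Plan will be assessed". Adverse events are the last item in that visit's list.

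The general rule in the same section is "The occurrence of Adverse Events will be assessed at each visit". Tab. 1 marks the adverse-event row at T0, T1, T2, T6, T10 and T24, with no column between T2 and T6. Section 4.10.2 also says that all adverse events from consent to the end of the study are to be recorded and reported.

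Two other sources of information operate between visits. For analgesic use, "a clinical diary will be given to the subject in which to indicate the day and the dose of drug used". Section 5.6 requires staff who hear of an adverse event from a subject to pass it to the investigator. The principal investigator then has 48 hours to report it to the sponsor, or at most 24 hours if it is serious.

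**The concern.** At T1 and T2 the plan ties the enquiry to the infiltration given a week earlier. The third infiltration has no equivalent check. Its first later enquiry falls at T6, whose date is that of an efficacy follow-up, and the documents give no reason for the longer interval.

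What is at stake is how complete and accurate the adverse-event record is. Section 5.6 grades non-serious events by whether they interfere with daily activities and whether they resolve without intervention. Those details and the onset date are harder to establish after four weeks than after one, and the events most exposed are brief and self-resolving. With no control arm, a reader of the final report may look informally at events by infiltration. Fewer events after the third could then be taken for better tolerance when the question was simply asked later.

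**Working it through.** The documents state no figure for the time from infiltration to adverse-event check, so there is none to reproduce. It follows from the visit days.

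**Inputs**

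- Infiltration days: 0, 7 and 14 (section 4.10.2; three weekly infiltrations in section 4.12).
- Adverse-event evaluation days, from the visit weeks in Tab. 1: T0 = 0, T1 = 7, T2 = 14, T6 = 6 × 7 = 42, T10 = 10 × 7 = 70, T24 = 24 × 7 = 168.
- Subjects: 49 (section 4.5).

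**Interval to the first scheduled check on a later day** = day of next evaluation − day of infiltration

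| Infiltration | Given on day | Next check on day | Interval |
|---|---|---|---|
| First | 0 | 7 | 7 − 0 = 7 days |
| Second | 7 | 14 | 14 − 7 = 7 days |
| Third | 14 | 42 | 42 − 14 = 28 days |

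The ratio is 28 / 7 = 4.

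**Infiltrations affected.** Planned total: 3 × 49 = 147. Third infiltrations: 49, and 49 / 147 = 33.3%. This assumes that every subject receives all three. It counts infiltrations under the longer interval, not events lost.

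**What covers days 14 to 42**

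- *Same-day evaluation at T2.* Tab. 1 marks one, so an immediate reaction could be noted. The documents do not say whether it comes before or after the infiltration, and the text for T2 looks back to the previous administration.
- *Spontaneous reports (section 5.6).* These work only if the subject makes contact.
- *Diary.* As described, it dates analgesic intake. Section 4.14.2 allows the analgesic for onset or recurrence of pain, so an entry does not separate a reaction to the infiltration from the underlying syndrome. A reaction treated without analgesic leaves no entry.
- *Recall at T6.* Up to 28 days.

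**Effect of one call at about day 21.** Interval after the third infiltration: 21 − 14 = 7 days, equal to the other two. From the call to T6: 42 − 21 = 21 days, which remain without a scheduled contact.

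**Size of the loss.** This would need an adverse-event rate and a recall loss at 7 and at 28 days. The documents give neither, so no estimate is offered.

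**The case against.** The strongest case on the other side is that nothing in the plan is contradicted. The 7-day checks arise because T1 and T2 are treatment visits, and equal look-back is nowhere promised. This is a single-arm, post-market pilot. Section 3.3 describes porcine collagen as unlikely to cause adverse effects. The only safety endpoint (sections 4.14.2 and 5.2.3) is the fraction of subjects who leave early in relation to adverse events. The reason for leaving is entered in the e-CRF (section 4.16), and a reaction forgotten by day 42 is unlikely to have caused a withdrawal. The diary form (Annex F) is not in the file and may already have a line for symptoms; instructions to subjects on reporting problems may also sit in pages not available here.

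Most of this stands, and it limits the point to completeness of the record. It does not remove the difference in intervals, or the fact that no enquiry is described between days 14 and 42.

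A reader might infer more than the documents support:

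- *That four-week recall is the sole source for reactions to the third infiltration.* Section 5.6 provides for spontaneous reports, Tab. 1 has an evaluation at T2 itself, and the diary gives an indirect trace of painful episodes.
- *That a per-infiltration event rate will be biased low.* The plan estimates no such rate, and under-recording is possible rather than shown.
- *That risk is highest after the third infiltration because exposure has accumulated.* Nothing in the documents supports a rising risk.
- *That a late infection would go unnoticed.* The documents give no onset window, serious events have a 24-hour reporting route, and a persisting problem would be seen at T6. A call at day 21 would not cover a later onset in any case.

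**Conclusion.** The point holds as a modest weakness in safety data collection. The first scheduled enquiry on a day after the third infiltration is four times as late as after the first two, for one third of planned infiltrations if all subjects complete the course. Brief reactions may be under-recorded against the plan's aim of recording every adverse event.

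The conclusion assumes that visits occur on their nominal days, that the diary holds no more than section 4.10.2 describes, and that no contact between T2 and T6 is specified in an annex not seen. The primary NRS endpoint does not use adverse-event records. Subjects who drop out count as failures whatever the reason (section 5.1), so sample size and power do not change, and the adverse-event dropout fraction is essentially unaffected. The change is worth making because it is cheap and the information cannot be recovered after data collection.

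**What to change.** 1. **Clinical diary (Annex F).** Add a dated adverse-event line with a description and resolved yes/no to the diary handed out at T0, unless the form already has one. State in section 4.10.2 that it is reviewed at every visit.
2. **Telephone contact.** Add one adverse-event call about 7 days after the third infiltration (around day 21), with its own entry in section 4.10.2 and its own column in Tab. 1, so that all three infiltrations have the same look-back.

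The cost is a revised diary page, an e-CRF page for the call, up to 49 short calls by existing staff, and an amendment submitted to the Ethics Committee under section 5.4. No visit, procedure, treatment or endpoint changes.

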4.3 Disign clinical investigation

This pilot single-centre clinical investigation will be based on a one-sample design. Variables will be assessed at 6 different times: at baseline (T0 time), after week 1, weeks 2, weeks 6, weeks 10 and after 24 weeks the start of the Clinical Investigation.

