4.6 Recruitment

Subjects will be enrolled after approval of the Clinical Investigation Plan by the relevant Ethics Committee of the ASST Istituto Ortopedico Gaetano Pini and notification of the study at the Ministry of Health.

Enrolment will involve subjects affected by GTPS, eligible according to the selection criteria. The diagnosis of GTPS will be made by the Principal Investigator through clinical examination and instrumental investigation of pelvis MRI for hips. The MRI examination must be recent and of good

quality; if the subject does not have one, an MRI examination will be performed prior to diagnosis and enrolment. Eligible subjects will be explained by a Co-Investigator the rationale of the Investigation Plan and the procedures involved. Consent to participate in the study will then be sought.

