4.14.2 Secondary End Points

- Evaluation of the NRS score at time weeks 6 and weeks 24 compared to time day 0.
- Evaluation of mHHS score at time weeks 6, weeks 10, and weeks 24 compared to time day 0.

_

- Clinical evaluation of abduction stenia at time weeks 6, weeks 10, and weeks 24 compared to time day 0.
 - [the stenia will be assessed, with the subject standing on the healthy limb, through measurements of the abduction force of the GTPS-affected hip, using a dynamometer]
- Evidence of resolution or decrease in inflammatory and degenerative signs of the peritrochanteric region of the GTPS-affected hip on MRI investigation at weeks 24 compared to day 0.
- Assessment of analgesic drug unit consumption based on clinical diary at day 0, week 1, week 2, weeks 6, weeks 10 and weeks 24.
 - [Celecoxib 200mg cpr 1 tablet/day will be used as a pain killer, in case of onset/recurrence of pain; if the subject is hypertensive or intolerant Paracetamol 1000mg cpr 2 tablets/day].
- Evaluation of the fraction of subjects who drop out of the Clinical Investigation Plan early in relation to Adverse Events (AE/SAE/SUSAR).

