4.15 Data collection

All data resulting from the Clinical Investigation will be entered, within seven days of their collection, into the electronic Data Collection Form (e-CRF) "Pheedit Dedagroup" provided by the

Sponsor. Radiological data will be collected and stored digitally on the PACS system. Data entry procedures will be performed by the Data Manager.

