5.2.3 Secondary Endpoints

Foreword: for all continuous variables, an attempt will always be made to use the parametric test; in the case of non-Gaussian distribution (possibly assessed after Shapiro-Wilk tests) or non-

homogeneous variance, an attempt will however be made to modify the variable with the use of a nonlinear transform (logarithm, ladder, etc.) before using the non-parametric equivalents.

The tests provided for the secondary endpoints are:

- NRS score assessment at time weeks 6 and weeks 24 compared to time day0: anova to repeated measures within subject or Friedman test.
- Evaluation of mHHS score time weeks 6, weeks 10, and weeks 24 compared to time day 0. Test Anova to repeated measures within subject or Friedman test.
- Clinical evaluation of stenia in abduction at time weeks 6, weeks 10, and weeks 24 compared to time day 0: Anova at repeated measurements within subject or Friedman's test
- Evidence of resolution or decrease in inflammatory and degenerative signs of the peritrochanteric region of the GTPS-affected hip, on MRI investigation at weeks 24 compared to day 0: Student's t-test for paired data or Wilcoxon test.
- Assessment of analgesic drug unit consumption based on clinical diary at day 0, week 1, weeks 2, weeks weeks 10, and weeks 24 compared to time day 0: repeated measures Anova or Friedman test.
- Assessment of the fraction of subjects leaving the clinical investigational early in relation to Adverse Events (AE/SAE/SUSAR): measurement of absolute and relative frequency and 95% confidence interval.

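### The MRI endpoint is read at day 0 and week 24 by the diagnosing investigator, with no masking of scan order and no defined grade, so reader expectation can enter the comparison

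*Combined protocol and SAP*

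**What the plan says.** Section 4.6 makes MRI part of the entry diagnosis: "The diagnosis of GTPS will be made by the Principal Investigator through clinical examination and instrumental investigation of pelvis MRI for hips". An existing scan may serve as baseline if it is recent and of good quality; how recent is not defined.

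Section 4.10.2 assigns "Diagnosis, evaluation of inflammatory and degenerative signs on MRI examination of the hip affected by GTPS and evaluation of pain on palpation" to a single named person. It requires at T24 "clinical evaluation and recording by MRI of signs of the inflammatory and degenerative state of the peritrochanteric region". Table 1 schedules MRI evaluation at T0 and T24 only, and palpation at T0, T6, T10 and T24.

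Section 4.14.2 words the secondary endpoint as "Evidence of resolution or decrease in inflammatory and degenerative signs of the peritrochanteric region" at week 24 against day 0. Section 5.2.3 plans a paired Student's t-test or a Wilcoxon test. Its rule of trying the parametric test first is written for continuous variables. Neither section defines an MRI score, grade or responder rule.

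On design, section 4.3 says: "This pilot single-centre clinical investigation will be based on a one-sample design". On storage, section 4.15 says: "Radiological data will be collected and stored digitally on the PACS system". No section mentions masked reading, randomised scan order, a second reader or a re-read.

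**The concern.** The day-0 scan is read while deciding whether the subject has GTPS and can be treated. The week-24 scan is evaluated at the closing visit by someone who has already palpated the hip at three visits and palpates it again at that one. A reader in that position will ordinarily know which scan came after treatment, and knows that every subject received the device.

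This matters because MRI is the only planned outcome that looks at tissue, and section 4.2 rests the rationale on tendon repair. In a controlled trial a general tendency to read later scans more favourably would affect both arms and largely cancel. Here nothing cancels it: any tilt in reading is added directly to the apparent effect. Without a stated grade, the reader also has wide latitude in deciding what counts as a decrease.

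**Working it through.** **1. Who reads what, and when.**

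| Step | Source | What it establishes |
|---|---|---|
| Diagnosis uses MRI | 4.6 | The baseline scan is read before treatment, for eligibility |
| Diagnosis, MRI evaluation and palpation by one person | 4.10.2 | The reader also examines the subject |
| MRI at T0 and T24 | Table 1 | The second read belongs to the end-of-study visit |
| One treated group | 4.3, 4.12 | No untreated scans are mixed in |
| Storage on PACS | 4.15 | A later re-read is feasible |
| Masking, order, grade | nowhere | Not planned or not defined |

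**2. The plan's own figures.** The documents give no figure for MRI. The only design calculation is for the primary endpoint (5.1). With n = 49, rejection at 19 or more successes, and rates of 25% and 50%, the exact binomial gives P(X ≥ 19 | 0.25) = 0.0231 and P(X ≥ 19 | 0.50) = 0.957. These match the stated 0.023 and 95.7%. MRI reading does not enter this calculation.

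**3. What a tilt in reading could do (illustration; all inputs assumed).** Assume 45 scan pairs, no true change, and reading noise that moves the grade in 40% of subjects. A share p+ is read as better and p− as worse, with p+ + p− = 0.40. Given m changed pairs, the number read as better is Binomial(m, p+/0.40), and m is Binomial(45, 0.40). Apply an exact two-sided sign test at 5% and sum the probability of rejecting in favour of improvement:

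| Better / worse | False improvement |
|---|---|
| 20% / 20% | 1.5% |
| 25% / 15% | 13.0% |
| 28% / 12% | 31.9% |
| 30% / 10% | 49.7% |

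The number of pairs matters little: the 25/15 result is 11.5% with 40 pairs and 14.0% with 49.

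**4. Does the choice between the listed tests matter?** In the same four scenarios, simulated with 45 pairs and one-grade shifts, the paired t-test and the Wilcoxon test falsely show improvement equally often: about 2%, 19%, 40% and 59%. Changing the test does not remove a reading bias.

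**5. Why the proportion improved is not enough.** With balanced noise and no true change, 0.20 × 45 = 9 subjects are read as improved. That is 9/45 = 20%, exact 95% CI 9.6% to 34.6%, an interval well above zero. Setting it beside an expected 9/45 worsened shows that there is no net change.

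**The case against.** **The documents never say the reader knows the scan order.** That is correct. It is tempting to state that the reader knows which scan is which, but that is an inference from the visit schedule and the shared roles. What the documents support is that no masking is planned. A masked re-read is not excluded either; it is simply absent.

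**A reader might infer that the endpoint is tested only by a paired t-test.** It is not. Section 5.2.3 also lists the Wilcoxon test, which would suit an ordinal grade, and the parametric-first rule is worded for continuous variables. The choice of test is not the defect. The gap is that no grade or responder rule exists for either test to use.

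**Randomised order might be thought to stop noise passing as healing.** It makes reading errors symmetric, so the comparison of better with worse becomes fair. The proportion improved, taken alone, still contains noise. Natural recovery also remains, because there is no control arm.

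**Re-reading by the same person is imperfect.** This stands. The reader may recall scans, and a baseline scan brought from elsewhere may be recognisable with its date removed. An independent reader would mask better but would need extra staff.

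**The size is assumed.** This also stands. The 45 pairs, the 40% shift rate and each tilt have no source in the documents. The figures show what a tilt would do, not that one is present or how large it is.

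**Conclusion.** The point holds in a limited form. One person diagnoses with MRI, palpates the hip and evaluates MRI at both time points in a single-arm study, and neither masking of scan order nor an MRI grade is specified. Reader expectation can therefore influence the week-24 versus day-0 result.

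Under the stated assumptions a moderate tilt (25/15) raises the false-improvement rate from 1.5% to 13%, and a strong one (30/10) to about 50%. These illustrate assumed bias and are not estimates for this trial.

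This is one of six secondary endpoints. The primary NRS endpoint, the sample size of 49 and the stated power do not change. It is a low-cost improvement that should be made, not a flaw that invalidates the study.

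**What to change.** **Section 4.10.2.** Add: after the last T24 visit, the same reader scores both stored scans of each subject on a pre-specified grade, with identity and date removed and order randomised; these scores are used for the endpoint. Name the grading scale, and define resolution and decrease in its terms.

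**Section 5.2.3.** For "on MRI investigation at weeks 24 compared to day 0", apply the already listed Wilcoxon signed-rank test to the grades. Report the proportions improved and worsened side by side, each with an exact 95% CI.

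**Cost.** One extra reading session for the existing reader, an anonymised export from PACS, and a few lines of protocol and SAP text. No extra staff, visits or subjects are needed. The MRI result becomes available only at study end. Masking will be partial, for the reasons given above, and the report should say so. It should also say that masked reading does not replace a control group.
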